#### **Statistical Analysis of Pharmacokinetic Parameters**

An analysis of variance (ANOVA) will be performed on the ln-transformed PK parameters AUC0-tauSS, and CmaxSS. The ANOVA model will include treatment as fixed effect. The results from the model will be back-transformed and the adjusted geometric means for each treatment and the estimated treatment ratios for the treatment comparisons will be presented together with 90% CIs.

The ratios and corresponding 90% CIs will be expressed as a percentage.

The following comparisons will be made:

GSP304 (tiotropium bromide) Inhalation Solution, [REDACTED]

GSP304 (tiotropium bromide) Inhalation Solution, [REDACTED]

GSP304 (tiotropium bromide) Inhalation Solution, [REDACTED]

For GSP304, dose-proportionality of tiotropium CmaxSS and AUC0-tauSS parameters will be assessed using a power model (linear regression relating log-transformed CmaxSS and AUC0-tauSS to the log-transformed dose). Estimates of the mean slopes of log-transformed dose will be reported along with corresponding 90% CIs. Dose proportionality will also be assessed based on amount of tiotropium excreted in urine.

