## 2. INTRODUCTION

The purpose of this statistical analysis plan (SAP) is to provide details of the planned statistical methodology for the analysis of the study data. The SAP also outlines the statistical programming specifications for the tables, listings and figures.

This SAP describes the study endpoints, derived variables, anticipated data transformations and manipulations, and other details of the analyses not provided in the study protocol. This SAP therefore outlines in detail all other aspects pertaining to the planned analyses and presentations for this study.

The following documents were reviewed in preparation of this SAP:

Protocol Revision Chronology:		
Protocol 1.0	11-Oct-2016	Original
Protocol 2.0	05-Jan-2017	Amendment 1
Protocol 3.0	11-Apr-2017	Amendment 2

This SAP was developed in accordance with ICH E9 guideline. All decisions regarding final analysis, as defined in this SAP document, will be made prior to Database Lock (unblinding) of the study data. Further information can be found in the protocol.

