### **8.4. Analysis of the Primary Pharmacokinetic Endpoints**

The primary endpoint,  $AUC_{0-\text{tauSS}}$ , and  $C_{\text{maxSS}}$ , will be analyzed using an analysis of variance (ANOVA) model. An ANOVA will be performed on the ln-transformed  $AUC_{0-\text{tauSS}}$ , and  $C_{\text{maxSS}}$ . The ANOVA model will include treatment as fixed effect. The results from the model will be back-transformed and the adjusted geometric means for each treatment and the estimated treatment ratios for the treatment comparisons will be presented together with 90% CIs. The ratios and corresponding 90% CIs will be expressed as a percentage. The following comparisons will be made:

- GSP304 █ vs Spiriva® Respimat®
- GSP304 █ vs Spiriva® Respimat®
- GSP304 █ vs Spiriva® Respimat®

The statements of a SAS® PROC MIXED analysis would be:

```
PROC GLIMMIX data=dataset;
  CLASS subject dose;
  MODEL log_normliased_pk_parameter= dose / ddfm=kr link=log;
  RANDOM intercept /subject= subject;
  ESTIMATE 'GSP1 vs Spiriva' dose 1 0 0 -1 /cl alpha=0.1;
  ESTIMATE 'GSP2 vs Spiriva' dose 0 1 0 -1 /cl alpha=0.1;
  ESTIMATE 'GSP3 vs Spiriva' dose 0 0 1 -1 /cl alpha=0.1;
  LSMEANS dose/diff cl ilink alpha=0.10
RUN;
```

The back-transformed and adjusted means for each treatment and the estimated treatment differences for the treatment comparisons will be presented together with 90% confidence intervals for the treatment comparisons. The adjusted means and estimated treatment differences for the treatment comparisons will also be plotted, with corresponding 90% confidence intervals.

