### **8.5. Exploratory Analysis**

#### **Dose-proportionality**

Dose-proportionality of tiotropium  $C_{\text{maxSS}}$  and  $AUC_{0-\text{tauSS}}$  parameters will be assessed using an ln-transformed power model:

$$\log_e Y_j = \alpha + \beta \log_e \text{dose}_j + \varepsilon_j,$$

where  $Y_j = C_{maxSS}$  or  $AUC_{0-\tau_{maxSS}}$  at  $j^{th}$  dose level. If  $\beta=0$ , then it implies that the response is independent from the dose and when  $\beta=1$ , dose-proportionality can be declared.

A mixed effect model can be used to fit the Power Model. Estimates of the mean slopes of log-transformed dose will be reported along with corresponding 90% CIs. If the 90% confidence interval for  $\beta$  is entirely contained within the *a priori* equivalence region, then dose proportionality is declared. If not, then dose non-proportionality is declared. Dose proportionality will be declared if the estimate of slope lies between 0.5- 2. Dose proportionality will also be assessed based on amount of tiotropium excreted in urine. Finally, dose normalized  $AUC_{0-\tau_{maxSS}}$  and  $C_{maxSS}$  will also be evaluated across doses. Dose proportionality will be confirmed if the dose normalized parameters remain substantially constant in the range of explored doses.

The statements of a SAS® PROC MIXED analysis would be:

```
PROC MIXED data=dataset;
  CLASS subject;
  MODEL log_pk_parameter= log_dose/ ddfm=kr;
  RANDOM intercept log_dose /subject=subject type=UN gcorr s;
  ESTIMATE 'Logdose - 1 unit' log_dose 1/cl alpha=0.1;
RUN;
```

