Parameter	Statistics	GSP304			Spiriva R 5 ug
		(N=xxx)	(N=xxx)	(N=xxx)	(N=xxx)
$C_{maxSS}$	n	xxx	xxx	xxx	xxx
	LS Mean (SE)	xx.x (xx.xx)	xx.x (xx.xx)	xx.x (xx.xx)	xx.x (xx.xx)
	Ratio[1] (SE)	xx.x (xx.xx)	xx.x (xx.xx)	xx.x (xx.xx)	xx.x (xx.xx)
	90% CI for Ratio	(xx.x, xx.x)	(xx.x, xx.x)	(xx.x, xx.x)	(xx.x, xx.x)
$AUC_{0-tauSS}$	n	xxx	xxx	xxx	xxx
	LS Mean (SE)	xx.x (xx.xx)	xx.x (xx.xx)	xx.x (xx.xx)	xx.x (xx.xx)
	Ratio[1] (SE)	xx.x (xx.xx)	xx.x (xx.xx)	xx.x (xx.xx)	xx.x (xx.xx)
	90% CI for Ratio	(xx.x, xx.x)	(xx.x, xx.x)	(xx.x, xx.x)	(xx.x, xx.x)

An ANOVA is performed on the ln-transformed  $AUC_{0-tauSS}$ , and  $C_{maxSS}$  and includes treatment as fixed effect. The results from the model are back-transformed.  
 [1] Ratio = GSP 304/ Spiriva; N = Number of PK subjects; n = Number of subjects with data in the summarized category

Program location/program name.sas/ddmmmyyyy/hh:mm

Source Data: Listing xxxxxxx Database Extract Date: ddmmmyyyy

Table 14.2.6  
Pharmacokinetics - Dose Proportionality Assessments of GSP304

PK Analysis Set

Power Model [1]	Parameter	Estimate(SE)	CI
$C_{maxSS}$	Intercept	xx.x (xx.xx)	(xx.x, xx.x)
	Slope	xx.x (xx.xx)	(xx.x, xx.x)
$AUC_{0-\tau SS}$	Intercept	xx.x (xx.xx)	(xx.x, xx.x)
	Slope	xx.x (xx.xx)	(xx.x, xx.x)
$A_{etau}$	Intercept	xx.x (xx.xx)	(xx.x, xx.x)
	Slope	xx.x (xx.xx)	(xx.x, xx.x)

[1] Exploratory Analysis: Dose-proportionality of tiotropium  $C_{maxSS}$ ,  $AUC_{0-\tau SS}$  and  $A_{etau}$  parameters is assessed using an ln-transformed power model. Dose proportionality will be declared if the estimate of slope lies between 0.5- 2.

Program location/program name.sas/ddmmmyyyy/hh:mm

Source Data: Listing xxxxxxx Database Extract Date: ddmmmyyyy

[figure not shown]
---

Programming notes:

---

Full Analysis Set

Figure 14.2.1.1  
Plot of LS Means of Change from Baseline in Day 21 Trough FEV1 (L)

Trough FEV1 is defined as the average of FEV1 obtained 23 hours 15 minutes and 23 hours 45 minutes post-morning dose of the previous day; LSM = Least Square Mean; n = Number of subjects with at least one post baseline visit in the summarized category; The model will include trough FEV1 from all visits (Days 1, 6, 13, 20 and Day 21) and fixed terms for treatment, visit, center, baseline, treatment by visit and baseline by visit interactions; Unstructured covariance structure is used;

Programming notes: Font for text/label number = 10pt; Only for Day 21

Repeat for

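### The SAS code in SAP Section 8.4 does not fit the stated ANOVA on ln-transformed AUC0-tauSS and CmaxSS, and taken as named it does not give geometric mean ratios

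*SAP*

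**What the plan says.** The text of SAP Section 8.4 specifies an ANOVA on the ln scale for AUC0-tauSS and CmaxSS. On the model terms it says "The ANOVA model will include treatment as fixed effect", and no other term is named. The Technical Summary Report gives the same method: "The results from the model will be back-transformed and the adjusted geometric means for each treatment", with treatment ratios and 90% confidence intervals. The footnote to the Table 14.2.5 shell in Section 12.2 agrees: the model is fitted to ln-transformed parameters "and includes treatment as fixed effect. The results from the model are back-transformed".

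The code printed in Section 8.4 contains these three lines:

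- "MODEL log_normliased_pk_parameter= dose / ddfm=kr link=log"
- "RANDOM intercept /subject= subject"
- "LSMEANS dose/diff cl ilink alpha=0.10"

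The power-model code in Section 8.5 also has a logged response, but no link option: "MODEL log_pk_parameter= log_dose/ ddfm=kr".

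Section 2 describes the status of such material: "The SAP also outlines the statistical programming specifications for the tables, listings and figures". Section 8.3 states that the primary PK endpoints are not formally tested.

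**The concern.** The code departs from the text in two ways that change the model. It applies a log link to a response whose name says it is already logged, and it adds a random subject intercept that the text never mentions. Section 10.9, which lists changes from the protocol, mentions no change to the PK model.

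Relative bioavailability is a primary objective. With no formal PK test, the ratios and 90% intervals in Table 14.2.5 are the whole reported result for it. If the code were followed as named, then over the range of geometric means examined below the ratios would be pulled towards 100%, so GSP304 and Spiriva would look more alike than they are. The answer would also change with the concentration unit.

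**Working it through.** The SAP has no PK mean, CV or expected ratio, so there is no figure of its own to reproduce. Every geometric mean (GM), CV and true ratio below is an assumption, chosen to show a range.

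**1. What each model estimates.** Write r for the true geometric mean ratio, GSP304 over Spiriva.

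- Stated ANOVA: exp(mean ln Y, GSP304 − mean ln Y, Spiriva) = r.
- Printed code, response logged as named: the link sets E[ln Y] = exp(η). ILINK therefore returns a mean log, and exp(η, GSP304 − η, Spiriva) = (mean ln Y, GSP304)/(mean ln Y, Spiriva) = ln(GM × r)/ln(GM) = 1 + ln r/ln(GM), where GM is the Spiriva geometric mean. The random intercept makes this approximate.

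The two agree at r = 1 but differ in general. The second depends on the unit through ln(GM), and the log link cannot represent a mean log that is zero or negative.

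**2. Numbers, logged reading, intercept ignored.** At GM 10 and r = 1.25: ln 12.5/ln 10 = 2.526/2.303 = 1.097.

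| True ratio | GM 5 | GM 10 | GM 200 |
|---|---|---|---|
| 80% | 86% | 90% | 96% |
| 125% | 114% | 110% | 104% |
| 200% | 143% | 130% | 113% |

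**3. Confidence intervals, logged reading, RANDOM line omitted.** With four arms of 28, GM 10 and 2000 runs per setting, the 90% interval covers a true 125% in 1, 20 and 48% of runs at CVs of 30, 50 and 80%. It covers a true 200% in 0% of runs at each CV. The stated ANOVA covers 89 to 90% in all six settings. A separate two-arm run (28 per arm, true 125%, CVs of 30 and 50%) gave mean code ratios of about 120, 110 and 105% at reference GMs of 3, 10 and 100. The stated ANOVA stayed at 125 to 125.5%.

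**4. Logged reading, RANDOM line kept.** The model Y = exp(μ + b) + e was fitted by marginal likelihood with 40-point quadrature (two arms of 28, GM 10, CV 50%, 60 data sets per ratio).

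| True ratio | Code | Ratio of mean logs | Geometric ratio, same data |
|---|---|---|---|
| 80% | 90.9% | 90.9% | 81.8% |
| 125% | 110.3% | 110.2% | 126.9% |
| 200% | 128.0% | 127.8% | 191.6% |

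The code's result was nearer the mean-log ratio than the geometric ratio in 55, 60 and 60 of the 60 data sets. The 191.6% benchmark is about 3 Monte Carlo standard errors low, so these averages are not precise; the direction is unaffected. SAS's default pseudo-likelihood fit was not run.

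**5. Unlogged reading, RANDOM line kept** (40 data sets each).

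| True ratio, CVs | Code | Geometric | Arithmetic |
|---|---|---|---|
| 125%, 50% v 80% | 119.7% | 123.2% | 107.8% |
| 125%, 50% both | 126.3% | 126.1% | 125.7% |
| 200%, 50% both | 198.5% | 202.0% | 201.0% |

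These results do not support a claim of bias on this reading.

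**6. The random intercept.** The trial is parallel group (Section 4.1), and both parameters are Day 21 quantities (Table 7), so each subject contributes one value per parameter. In the identity-link normal model the log-likelihood was −28.26 for every split tested of a total variance of 0.16 (between-subject part 0, 0.04, 0.08 or 0.12). A subject intercept cannot be separated from the residual there.

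**7. Which reading the SAP supports.** The Section 8.5 code uses `log_pk_parameter` for the ln-transformed response with no link option. By that convention the `log_` prefix in Section 8.4 marks a logged variable, though the misspelled remainder of the name leaves some doubt.

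**The case against.** The strongest reply is that the SAP states the correct analysis in several places and the code is only a sketch. The Technical Summary Report, Section 8.4 and the Table 14.2.5 footnote all agree. The code is introduced conditionally, announces PROC MIXED but shows PROC GLIMMIX, and lacks a semicolon before RUN, so someone must repair it with the right text directly above. Its ESTIMATE lines carry no exponentiation, so the wrong ratio appears only if the back-transformation text is obeyed and the ln-ANOVA text is not.

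The error should also be visible. With treatment as the only effect and the same subjects, the adjusted geometric mean equals the arm's descriptive geometric mean, which Section 8.2 requires. On the logged reading Table 14.2.5 would show about 2.3 (ln 10) where the descriptive table shows 10, and Section 6.3 calls for independent checking. Every PK value used above is assumed, and no decision limit attaches to the ratios.

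Most of this stands as a reason why harm is less likely. It does not make the code right. Adding the semicolon leaves the link and the RANDOM line in place. A programmer who does notice must override code the SAP itself supplies.

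**Conclusion.** The concern holds: on either reading of the response name, the printed code is not the ANOVA that Section 8.4 states. That conclusion needs no assumption about PK values.

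The numerical consequence depends on the response being logged, as its name and the Section 8.5 convention suggest. On that reading, over assumed Spiriva geometric means of 5 to 200, a true 125% would be reported as 114 to 104%, and a true 200% as 143 to 113%. On the unlogged reading the result may be close to the planned ratio.

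The stated method, comparisons and confidence level are sound; the fault is confined to the code. Because that code is the only one supplied for the primary PK result, it should be corrected before the analysis is programmed.

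**What to change.** Rewrite the Section 8.4 code to match its text:

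- Fit ln(AUC0-tauSS) and ln(CmaxSS), not dose-normalised, on treatment alone with an identity link, using PROC MIXED or PROC GLM.
- Delete `link=log` and the RANDOM statement.
- Name the response so that its scale is unambiguous.
- Exponentiate each GSP304-minus-Spiriva difference and its 90% limits, and multiply by 100.

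Editorial points to correct at the same time: make the procedure named in the lead-in match the code, add the missing semicolon after the LSMEANS line, and align the AUC unit, which is ng.h/mL in Listings 16.2.6.2.3 and 16.2.6.2.4 but pg*hr/mL in Table 14.2.4.1.

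The cost is a few lines of SAP code. No patients and no data collection are affected.

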### **8.5. Exploratory Analysis**

#### **Dose-proportionality**

Dose-proportionality of tiotropium  $C_{\text{maxSS}}$  and  $AUC_{0-\text{tauSS}}$  parameters will be assessed using an ln-transformed power model:

$$\log_e Y_j = \alpha + \beta \log_e \text{dose}_j + \varepsilon_j,$$

where  $Y_j = C_{maxSS}$  or  $AUC_{0-\tau_{maxSS}}$  at  $j^{th}$  dose level. If  $\beta=0$ , then it implies that the response is independent from the dose and when  $\beta=1$ , dose-proportionality can be declared.

A mixed effect model can be used to fit the Power Model. Estimates of the mean slopes of log-transformed dose will be reported along with corresponding 90% CIs. If the 90% confidence interval for  $\beta$  is entirely contained within the *a priori* equivalence region, then dose proportionality is declared. If not, then dose non-proportionality is declared. Dose proportionality will be declared if the estimate of slope lies between 0.5- 2. Dose proportionality will also be assessed based on amount of tiotropium excreted in urine. Finally, dose normalized  $AUC_{0-\tau_{maxSS}}$  and  $C_{maxSS}$  will also be evaluated across doses. Dose proportionality will be confirmed if the dose normalized parameters remain substantially constant in the range of explored doses.

The statements of a SAS® PROC MIXED analysis would be:

```
PROC MIXED data=dataset;
  CLASS subject;
  MODEL log_pk_parameter= log_dose/ ddfm=kr;
  RANDOM intercept log_dose /subject=subject type=UN gcorr s;
  ESTIMATE 'Logdose - 1 unit' log_dose 1/cl alpha=0.1;
RUN;
```

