## 4. STUDY DESIGN

### 4.1. Summary of Study Design

This is a phase 2, randomized, parallel group, active-and placebo-controlled, 5-arm study to compare the PK profile of 3 blinded doses of GSP304 with open label Spiriva® Respimat®. The study will also evaluate the dose response PD profile of 3 blinded doses of GSP304 compared with blinded GSP304 placebo, using spirometry in subjects with mild to moderate COPD.

The study will consist of a screening period of up to 2 weeks, followed by a 2-week run-in period, a 3-week treatment period, and a 2-week post treatment follow-up period. The total duration of study participation will be approximately 9 weeks.

A total of 155 male and female subjects will be randomized in a 1:1:1:1:1 ratio to 1 of 5 treatment arms. A subject will receive 1 of the 3 double-blind doses of GSP304, or double-blind GSP304 placebo, or open-label Spiriva® Respimat®.

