### **4.3. Sample Size Considerations**

#### **4.3.1. Sample Size Justifications**

A sample size of 28 subjects per treatment arm will have 90% power to detect a difference in mean change from baseline in trough FEV1 of 150 mL between GSP304 and GSP304 placebo assuming a 2-sided alpha of 5% and a standard deviation (SD) of 170 mL. These assumptions are based on available literature from similar studies conducted for Spiriva® Respimat® (Caillaud et al., 2007). Given the overall 1:1:1:1:1 study treatment allocation ratio, 140 subjects are required for the analysis of the primary endpoint. Assuming a dropout rate of 10%, a total of 155 subjects (31 subjects per treatment arm) will be randomized.

This sample size is also considered to be sufficient for the relative bioavailability endpoint.

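### The 0.5 to 2 slope limits for declaring dose proportionality are lopsided around 1 and ignore the dose range, so they can pass a marked departure from proportionality

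*SAP*

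**What the plan says.** Under Dose-proportionality in section 8.5, the SAP says that CmaxSS and AUC0-tauSS "parameters will be assessed using an ln-transformed power model", ln Y = alpha + beta ln dose. It takes beta = 1 as proportionality and beta = 0 as no dependence on dose. It adds that "Estimates of the mean slopes of log-transformed dose will be reported along with corresponding 90% CIs".

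Three criteria follow in one paragraph:

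- The 90% CI for beta is to lie in a pre-set "equivalence region, then dose proportionality is declared. If not, then dose non-proportionality is declared". No figures are attached to that region.
- "Dose proportionality will be declared if the estimate of slope lies between 0.5- 2". This is the only rule with numbers. It is repeated in footnote [1] of Table 14.2.6, which also covers urinary Aetau.
- "Dose proportionality will be confirmed if the dose normalized parameters remain substantially constant in the range of explored doses". This has no figure.

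No derivation of 0.5 and 2 is given, and the dose range does not enter them.

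**The concern.** A power-model slope is an exponent. Its distance from 1 translates into a fold change in dose-normalised exposure only through the dose ratio. Limits of 0.5 and 2 are reciprocals of each other, so they look even-handed, but on the slope scale they are not: the room above 1 is twice the room below it. Because r is absent, the same two numbers also tolerate very different departures depending on how far apart the doses are.

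Section 8.3 rules out formal testing of the primary PK endpoints, and section 8.4 sets no acceptance limits for the ratios to Spiriva. Dose proportionality is therefore the one PK result with a declare-or-not rule. At stake is whether that declaration means anything definite, and whether it can be made while the dose-normalised values in the same report rise with dose.

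**Working it through.** **Inputs.** From the SAP: the power model, the limits 0.5 and 2, the 90% level, three GSP304 doses (section 4.1) and 28 subjects per arm (section 4.3.1). The 28 was checked: a difference of 150 mL, SD 170 mL and two-sided 5% give a t-test power of 0.900. Assumed: 28 per arm evaluable for PK, doses equally spaced on the log scale, between-subject CV 30-100%, and r from 1.5 to 8, because the doses are redacted and no PK variability is stated.

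**Step 1: what the limits allow.** If Y is proportional to dose^beta, then Y/dose is proportional to dose^(beta-1). The high-to-low ratio of dose-normalised exposure is r^(beta-1), so slopes of 0.5 and 2 correspond to r^-0.5 and r.

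| r | ratio at slope 0.5 | ratio at slope 2 |
|---|---|---|
| 2 | 0.71 | 2 |
| 3 | 0.58 | 3 |
| 4 | 0.50 | 4 |
| 8 | 0.35 | 8 |

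Whatever the doses are, at a slope of 2 each doubling of dose multiplies exposure by 2^2 = 4, twice the proportional amount.

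**Step 2: can the limits be reproduced?** A reciprocal tolerance (1/theta, theta) on the dose-normalised ratio gives slope limits 1 - ln(theta)/ln(r) and 1 + ln(theta)/ln(r), which are symmetric about 1. With theta = 2, a lower limit of 0.5 needs ln 2/ln r = 0.5, so r = 4. An upper limit of 2 needs ln 2/ln r = 1, so r = 2. No single dose range gives both.

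**Step 3: chance of declaring proportionality when dose-normalised exposure truly doubles.** The true slope is 1 + ln 2/ln r. With log doses at -0.5, 0 and 0.5 times ln r, the sum of squares is 28 × 2 × (0.5 ln r)^2 = 14 (ln r)^2. Hence SE = sigma/(ln r × √14), with sigma = √ln(1 + CV^2), which is 0.294, 0.472 and 0.833 at CV 30%, 50% and 100%.

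Worked case, r = 3 and CV 100%: true slope 1.631; SE = 0.833/(1.099 × 3.742) = 0.203.

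- Estimate rule: (2 - 1.631)/0.203 = 1.82, giving 97%.
- 90% CI compared with 0.5 to 2: the half-width is 1.664 × 0.203 = 0.338 (t, 82 df), and (2 - 0.338 - 1.631)/0.203 = 0.15, giving 56%.

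| r | true slope | estimate in 0.5-2 | 90% CI in 0.5-2 |
|---|---|---|---|
| 1.5 | 2.71 | 0-10% | 0% |
| 2 | 2.00 | 50% | about 5% |
| 3 | 1.63 | 97-100% | 56-100% |
| 4 to 8 | 1.50 to 1.33 | about 100% | 93-100% |

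**Step 4: the asymmetry in practice.** At r = 4 and CV 50% (SE 0.091), a true doubling (slope 1.5) passes in about 100% of trials under either rule. A true halving (slope 0.5) passes in 50% by estimate and 5% by CI.

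**The case against.** The strongest reply is that little hangs on this. The analysis is labelled exploratory in section 8.5, Table 10 and the Table 14.2.6 footnote, and no decision in the SAP depends on it. The slope and its 90% CI, the dose-normalised parameters and the ratios to Spiriva are all reported, so a reader would see a slope of 1.5 or 2. This stands. It confines the harm to the declared conclusion, and it does not support the stronger inference that exposure at the higher doses would be hidden.

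A reader might also infer that more-than-proportional exposure is almost always declared proportional. The documents do not support that. The result turns on redacted doses: a doubling passes in at most 10% of trials at r = 1.5 and 50% at r = 2.

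Nor can it be said that the fault is the same under a CI rule. The SAP ties 0.5 and 2 to the estimate and leaves its CI region without figures, so the CI column above tests a rule that the SAP does not clearly state. Even then the rate falls to 56% at r = 3 with CV 100%.

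That the limits were borrowed from a fold-ratio range is likewise only an inference from their reciprocal form. The SAP gives no origin, and the arithmetic does not need one.

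Finally, the check on dose-normalised parameters points against a false declaration. It does, but without a figure it cannot be relied on to override a numerical rule that says the opposite.

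**Conclusion.** The point holds as a flaw in a stated decision threshold. At any dose ratio above 1, the limits are asymmetric about a slope of 1, take no account of the dose range, and allow dose-normalised exposure to rise up to r-fold while the paragraph also asks for it to stay essentially flat. These statements follow from the SAP's own model.

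The error rates are conditional on 28 evaluable subjects per arm, log-equal spacing, CV 30-100% and the assumed r. Under the written estimate rule, the chance of declaring proportionality when dose-normalised exposure doubles becomes serious from r = 2 (50%) and is near certain at r = 3 and above (97-100%). If the sponsor's doses span less than a factor of two, a doubling is mostly caught, though the asymmetry remains. Since the analysis is exploratory and its estimates are printed, this should be corrected but does not threaten the trial's primary results.

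**What to change.** In section 8.5 and the Table 14.2.6 footnote, replace 0.5 to 2 with one rule: proportionality is declared if the 90% CI for beta lies within 1 - ln(theta)/ln(r) to 1 + ln(theta)/ln(r), with r taken from the study's own doses. Use the same range (1/theta, theta) for r^(beta-1) as the numerical meaning of the dose-normalised criterion, and print r^(beta-1) with its 90% CI in Table 14.2.6.

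Fix theta before unblinding, so that neither slope limit is looser than the present 0.5 or 2 and the lower limit stays well above 0. A lower limit of at least 0.5 requires ln(theta)/ln(r) ≤ 0.5, that is theta ≤ √r: at most 1.41 at r = 2, 1.73 at r = 3 and 2 at r = 4. Theta = 2 is therefore unsuitable below r = 4. At r = 2 it gives limits of 0 to 2: the upper limit is unchanged, the lower limit is the value that the SAP itself equates with no dose dependence, and a true slope of 0.3 would pass about 49% of the time at CV 50%.

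The cost is SAP wording in one section, one footnote and one derived line; no new data are needed. Proportionality will be declared less readily, and with a narrow dose range or high CV the result may be inconclusive. For example, with r = 2, CV 100% and limits of 0.5 to 1.5, SE = 0.833/(0.693 × 3.742) = 0.321, so the CI half-width is 1.664 × 0.321 = 0.53. That exceeds 0.5, so at that residual SD the interval cannot fit. Failure to meet the rule should then be reported as not shown, not as proof of non-proportionality.

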**Table 6: Plasma Pharmacokinetic Parameters (Day 1)**

Parameter	Definition
AUC 0-tau	Area under the concentration-time profile over the dosing interval
C max	Peak concentrations during the dosing interval
t last	Time of last quantifiable concentration
t max	Time of peak drug concentration

The PK parameters in Table 7 will be determined for Tiotropium in plasma following multiple dose administration (Day 21). The terminal elimination half-life will be reported only if data permit a reliable estimation.

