Y-axis = Parameter (unit) =  $A_{etau}$  (day 1 and day 21)

Page XX of YY

Table 14.3.1.1  
 Overall Summary of Adverse Events

Safety Set

	GSP304					Spiriva R	
	(N=xxx) n (%) [#]	(N=xxx) n (%) [#]	(N=xxx) n (%) [#]	Total (N=xxx) n (%) [#]	Placebo (N=xxx) n (%) [#]	5 ug (N=xxx) n (%) [#]	Total (N=xxx) n (%) [#]
TEAEs	xx (xx.x) [#]	xx (xx.x) [#]	xx (xx.x) [#]	xx (xx.x) [#]	xx (xx.x) [#]	xx (xx.x) [#]	xx (xx.x) [#]
TEAEs Leading to Discontinuation [1]	xx (xx.x) [#]	xx (xx.x) [#]	xx (xx.x) [#]	xx (xx.x) [#]	xx (xx.x) [#]	xx (xx.x) [#]	xx (xx.x) [#]
TEAEs Related to Study Drug	xx (xx.x) [#]	xx (xx.x) [#]	xx (xx.x) [#]	xx (xx.x) [#]	xx (xx.x) [#]	xx (xx.x) [#]	xx (xx.x) [#]
AEs Leading to Withdrawal [2]	xx (xx.x) [#]	xx (xx.x) [#]	xx (xx.x) [#]	xx (xx.x) [#]	xx (xx.x) [#]	xx (xx.x) [#]	xx (xx.x) [#]
SAE	xx (xx.x) [#]	xx (xx.x) [#]	xx (xx.x) [#]	xx (xx.x) [#]	xx (xx.x) [#]	xx (xx.x) [#]	xx (xx.x) [#]
SAE Seriousness Reasons							
Congenital Anomaly or Birth Defect	xx (xx.x) [#]	xx (xx.x) [#]	xx (xx.x) [#]	xx (xx.x) [#]	xx (xx.x) [#]	xx (xx.x) [#]	xx (xx.x) [#]
Persistent or Significant Disability or Incapacity	xx (xx.x) [#]	xx (xx.x) [#]	xx (xx.x) [#]	xx (xx.x) [#]	xx (xx.x) [#]	xx (xx.x) [#]	xx (xx.x) [#]
Death	xx (xx.x) [#]	xx (xx.x) [#]	xx (xx.x) [#]	xx (xx.x) [#]	xx (xx.x) [#]	xx (xx.x) [#]	xx (xx.x) [#]
Initial or Prolonged Hospitalization	xx (xx.x) [#]	xx (xx.x) [#]	xx (xx.x) [#]	xx (xx.x) [#]	xx (xx.x) [#]	xx (xx.x) [#]	xx (xx.x) [#]
Medically Important Event	xx (xx.x) [#]	xx (xx.x) [#]	xx (xx.x) [#]	xx (xx.x) [#]	xx (xx.x) [#]	xx (xx.x) [#]	xx (xx.x) [#]
Life Threatening	xx (xx.x) [#]	xx (xx.x) [#]	xx (xx.x) [#]	xx (xx.x) [#]	xx (xx.x) [#]	xx (xx.x) [#]	xx (xx.x) [#]
SAEs Related to Study Drug	xx (xx.x) [#]	xx (xx.x) [#]	xx (xx.x) [#]	xx (xx.x) [#]	xx (xx.x) [#]	xx (xx.x) [#]	xx (xx.x) [#]

AE = Adverse Events; SAE = Serious Adverse Events; TEAE = Treatment-Emergent Adverse Events; TEAEs are defined as AEs (identified by PT) that begins or that worsens in severity after at least one dose of study treatment has been administered, up to the last study visit; PT = Preferred Term; n = Number of subjects reporting at least one TEAE in that category; [#] = Number of individual occurrences of the TEAE in that category

[1] counts all TEAEs leading to study discontinuation or treatment discontinuation during treatment period or follow-up period

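### The power-model code in SAP 8.5 gives each subject a random intercept and random dose slope, which one dose and one Day 21 value per subject cannot support and the stated regression does not contain

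*SAP*

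**What the plan says.** The SAP describes the dose-proportionality model in three places.

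- **Synopsis, Statistical Analysis of Pharmacokinetic Parameters:** proportionality "will be assessed using a power model (linear regression relating log-transformed" CmaxSS and AUC0-tauSS to log dose.
- **Section 8.5, equation:** the log parameter equals alpha plus beta times log dose plus a single error term.
- **Section 8.5, text and code:** "A mixed effect model can be used to fit the Power Model", followed by PROC MIXED statements containing "MODEL log_pk_parameter= log_dose/ ddfm=kr" and "RANDOM intercept log_dose /subject=subject type=UN gcorr s". This is the only implementation given.

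Two features of the design bear on it. Section 4.1 is a parallel-group design: "A subject will receive 1 of the 3 double-blind doses of GSP304, or double-blind GSP304 placebo, or open-label Spiriva® Respimat". Section 6.7.6 derives the steady-state parameters "following multiple dose administration (Day 21" only, so each GSP304 subject supplies one record per parameter at one dose.

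**The concern.** A model with a subject-specific intercept and slope needs several doses within a subject. Here log dose never varies within a subject and there is no replicate. The code asks for three random-effect parameters (two variances and a covariance) plus a residual variance, from data that can reveal only how much subjects vary at each of three doses.

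The 90% CI of the slope is reported in Table 14.2.6 and enters one of the proportionality rules in 8.5. Code that cannot be fitted cleanly would force a model choice after database lock. Sections 9.6.1 and 9.7 say what to do if the MMRM fails to converge; 8.5 gives no such instruction.

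**Working it through.** **Inputs from the SAP.** Three GSP304 doses, one per subject; one Day 21 value per parameter; 28 evaluable subjects per arm (section 4.3.1); 90% CI. The figure of 28 reproduces: 150 mL, SD 170 mL, two-sided 5% and 90% power give 27.99 per arm by the two-sample t calculation. It serves here only as n per dose.

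**Assumed inputs.** The doses are redacted and no PK variability is given. I took dose ratios 1:2:4, 1:2:3 and 1:3:9, CVs of 30%, 50% and 80%, and 25 or 28 subjects per dose.

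**Identifiability.** With x = ln(dose) and one record per subject, the code implies

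Var(ln Y) = g11 + 2·g12·x + g22·x² + s2.

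g11 and s2 appear only as a sum. Three doses give three variances for four parameters, and the design matrix had rank 3 of 4 for every dose set tried. This does not depend on the redacted doses.

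In one simulated dataset (1:2:4, 28 per dose, CV 50%) three starting values, with variances unbounded, gave:

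| g11 | s2 | g11 + s2 | Slope | SE |
|---|---|---|---|---|
| 0.0207 | 0.1472 | 0.1679 | 0.96307 | 0.07698 |
| -0.3213 | 0.4892 | 0.1679 | 0.96307 | 0.07698 |
| 0.0242 | 0.1437 | 0.1679 | 0.96307 | 0.07698 |

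The REML log-likelihood was the same each time. One Hessian eigenvalue was about zero (3.6e-07, the others 47 to 9696). The variance split is arbitrary; the slope and its SE are not. Ordinary regression on the same data gave 0.96464, SE 0.07848.

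**Ordinary regression as benchmark.** At CV 50% the log-scale SD is √ln(1.25) = 0.472. For doses 1:2:4 with 28 each, the sum of squares of x is 28 × 2 × (ln 2)² = 26.9. So SE = 0.472/√26.9 = 0.091, and with 84 − 2 = 82 df the 90% CI width is 2 × 1.664 × 0.091 = 0.303.

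**Effect on the slope CI.** Data were simulated with true slope 1 and constant variance, 1,500 datasets per row. In the RANDOM columns the variances were unbounded, so each dose has its own variance.

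| Doses | n per dose | CV | Coverage, regression | Coverage, RANDOM (t / normal quantile) | Mean width, regression / RANDOM |
|---|---|---|---|---|---|
| 1:2:4 | 28 | 50% | 0.909 | 0.907 / 0.901 | 0.302 / 0.299 |
| 1:2:4 | 28 | 30% | 0.900 | 0.900 / 0.897 | 0.188 / 0.186 |
| 1:2:3 | 28 | 80% | 0.899 | 0.893 / 0.886 | 0.560 / 0.556 |
| 1:3:9 | 25 | 50% | 0.898 | 0.894 / 0.891 | 0.202 / 0.199 |

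The Monte Carlo standard error is √(0.9 × 0.1/1500) = 0.008.

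The first three settings were repeated with variances bounded at zero and Satterthwaite df from a generalised inverse (1,200 datasets each). Coverage was 0.898 to 0.913. Median df was about 57 to 65 against 82, which moves the 90% t quantile only from about 1.664 to 1.672. The slope variance sat at zero in 45% to 49% of datasets. The SE relative to regression had a median of 1.00 to 1.01, with 5th to 95th percentiles between 0.95 and 1.08.

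**The case against.** A reader might infer that, because the model is not identifiable, the slope CI cannot be trusted or depends on where the optimiser stops. The documents and the check do not support that. What is unidentified is how total variance is divided between subject intercept and residual. Every division gives the same variance at each dose, hence the same slope and SE, and coverage stayed close to 90%.

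Other mitigating points also stand. The analysis is headed exploratory, and section 8.3 plans no formal test on the primary PK endpoints. The mixed model is permitted rather than required. Table 14.2.6 reports only intercept and slope, so no arbitrary variance component enters a planned result. Section 8.5 also states a point-estimate rule for the slope, so the CI is not the only criterion.

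These points limit the consequence without making the code right. No other implementation is offered, and the code and the equation describe different models. The code fits a regression with dose-dependent variance that nobody specified, and in a single dataset it can move the SE by 5% down or 8% up.

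A reader might also extend the point to urinary Aetau, which the Figure 14.2.5.2 template shows for "day 1 and day 21". That would go too far: the figure template is panelled by day and the SAP does not say that the two days are pooled.

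**Conclusion.** The RANDOM statement is mis-specified for this design and contradicts both the equation in 8.5 and the synopsis. Four covariance parameters are requested and three can be identified, whatever the redacted doses are. The real consequences are:

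- arbitrary variance components, and with them the random-effect correlation and solutions that the code prints;
- a likely non-positive-definite or non-convergence message, with no fallback in 8.5;
- Kenward-Roger df computed from a singular information matrix.

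If the fit converges, the slope and its 90% CI are nearly those of ordinary regression. That conclusion on size rests on the assumed doses and CVs, on constant true variance, and on a Satterthwaite substitute for the df; Kenward-Roger in SAS was not run. The impact is limited to an exploratory analysis and does not touch the primary PK comparison with Spiriva or the FEV1 endpoint.

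**What to change.** In section 8.5, delete the RANDOM statement and the sentence "A mixed effect model can be used to fit the Power Model". State that ln(parameter) = alpha + beta·ln(dose) + error is fitted by ordinary least squares, with the 90% CI for beta from the t distribution on n − 2 df (82 df at 28 subjects in each of three doses). Kenward-Roger df are then unnecessary. The code, the equation and the synopsis will agree, and no convergence fallback is needed.

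The cost is one sentence and a small edit to the code, with no loss of data or power.
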